A vertical column of 20 black horizontal bars of varying lengths, representing a data series. The bars are positioned on the right side of the page, with a vertical line to the left and a small black square at the top left.

Statistical Analysis Plan of PTCL (Version 3.0)

Protocol Code: DZ2019J0005 (Part B)

Date: Mar 25, 2023

Statistical Analysis Plan of PTCL (Version 3.0)

Protocol Code: DZ2019J0005 (Part B)

Date: Mar 25, 2023

LIST OF ABBREVIATIONS

Abbreviation	Full Term
ADI	Actual Dose Intensity
AE	Adverse Event
ALP	Alkaline Phosphatase
ALT	Alanine Aminotransferase
aPTT	activated Partial Thromboplastin Time
AST	Aspartate Aminotransferase
ATC	Anatomical Therapeutic Chemical
AUC ₍₀₋₂₄₎	Area Under the Plasma Concentration-Time Curve from 0 to 24 Hours
AUC _(0-t)	Area Under the Plasma Concentration-Time Curve from 0 to the Time of the Last Measurable Concentration
AUC _{ss}	Area Under the Plasma Concentration-Time Curve from 0 to the End of Dosing Interval
BLQ	Below the Limit of Quantification
BMI	Body Mass Index
BOR	Best Overall Response
CI	Confidence Interval
CL _{ss} /F	Apparent Plasma Clearance at Steady State
C _{max}	Maximum Plasma Concentration
CM	Concomitant Medication
CR	Complete Response
CRF	Case Report Form
CRR	Complete Response Rate
CSP	Clinical Study Protocol
CSR	Clinical Study Report
C _{ss max}	Maximum Plasma Concentration at Steady State
C _{ss min}	Minimum Plasma Concentration at Steady State
CTCAE	Common Terminology Criteria for Adverse Events
CV	Coefficient of Variation
DoR	Duration of Response
DLCO	Diffusing Capacity of Lung for Carbon Monoxide
ECG	Electrocardiogram
ECOG	Eastern Co-operative Oncology Group
EDC	Electronic Data Capture

Statistical Analysis Plan of PTCL (Version 3.0)

Protocol Code: DZ2019J0005 (Part B)

Date: Mar 25, 2023

Abbreviation	Full Term
FEV1	Forced Expiratory Volume in 1 Second
FEV1PP	Percent Predicted FEV1
FVC	Forced Vital Capacity
ICH	International Council for Harmonisation
INR	International Normalized Ratio
IRC	Independent Review Committee
LDH	Lactate Dehydrogenase
LLN	Lower Limit of Normal
LVEF	Left Ventricular Ejection Fraction
LLOQ	Lower Limit of Quantification
MedDRA	Medical Dictionary for Regulatory Activities
MUGA	Multi-gated Acquisition Scan
NC	Not Calculable
NCI-CTCAE	National Cancer Institute-Common Terminology Criteria for Adverse Events
NE	Not Evaluable
NQ	Not Quantifiable
ORR	Objective Response Rate
OS	Overall Survival
PD	Progressive Disease
PFS	Progression Free Survival
PFT	Pulmonary Function Test
PK	Pharmacokinetics
PKS	Pharmacokinetics Set
PT	Preferred Term
PTCL	Peripheral T-cell lymphoma
QD	Once Daily
QTcF	Fridericia Corrected QT
RDI	Relative Dose Intensity
r/r PTCL	Relapsed or Refractory Peripheral T-cell Lymphoma
SAE	Serious Adverse Event
SAP	Statistical Analysis Plan
SAS	Statistical Analysis System
SD	Standard Deviation
SD	Stable Disease

Statistical Analysis Plan of PTCL (Version 3.0)

Protocol Code: DZ2019J0005 (Part B)

Date: Mar 25, 2023

Abbreviation	Full Term
SOC	System Organ Class
SPD	Sum of the Product of the Perpendicular Diameters
TEAE	Treatment-emergent Adverse Event
TESAE	Treatment-emergent Serious Adverse Event
TLG	Table, Listing and Graph
T _{max}	Time to C _{max}
T _{ss max}	Time to C _{ss max}
TTR	Time to Response
ULN	Upper Limit of Normal

Statistical Analysis Plan of PTCL (Version 3.0)

Protocol Code: DZ2019J0005 (Part B)

Date: Mar 25, 2023

1. INTRODUCTION

This Statistical Analysis Plan (SAP) describes the analyses required for Part B of study DZ2019J0005, which is a phase 2, open-label, single-arm, pivotal study of AZD4205 treating patients with relapsed or refractory peripheral T-cell lymphoma (r/r PTCL). The statistical analyses required for part A of DZ2019J0005 (phase 1) were documented in a separate analysis plan.

The SAP contains a more technical and detailed elaboration of the analysis described in the Clinical Study Protocol (CSP). It also includes detailed procedures for executing the statistical analysis required.

The SAP was written based on the following documents:

Document	Version #	Date
CSP	5.0	November 25, 2020
Case Report Form (CRF)	3.0	January 28, 2021
Independent Review Charter	2.0	July 02, 2021

2. OVERVIEW AND INVESTIGATIONAL PLAN

2.1 Study Objectives and Endpoints/Estimand

The objectives of Part B of study DZ2019J0005 are listed below.

2.1.1 Primary Objective, Endpoint and Estimand

Primary Objective	Endpoint/Variable

To assess the anti-tumor efficacy of AZD4205 using CT-based objective response rate (ORR) as primary efficacy endpoint in patients with r/r PTCL	
CT-based ORR evaluated by independent review committee (IRC), according to 2014 Lugano classification

Estimand of primary objective

Treatment: Participants will receive AZD4205 capsule.

Population: Patients with relapsed or refractory peripheral T-cell lymphoma (PTCL). Evaluable for CT-based response set will be used for analysis, including all dosed central pathology confirmed PTCL participants with baseline measurable disease confirmed by IRC using CT imaging.

Statistical Analysis Plan of PTCL (Version 3.0)

Protocol Code: DZ2019J0005 (Part B)

Date: Mar 25, 2023

Variable (or endpoint): Binary variable indicating whether a participant is a responder who achieved complete response (CR) or partial response (PR), evaluated by IRC based on CT imaging according to Lugano criteria.

Intercurrent Events and strategies:

Intercurrent Events	Strategies for ORR
Discontinuation of study treatment due to reasons other than progressive disease (PD)	Treatment policy: Occurrence of intercurrent event ignored.
PD	While on treatment: The intercurrent event is already captured in the variable definition.
New anti-cancer therapy	While on treatment: Response to treatment prior to the occurrence of the intercurrent event is of interest.

Population-level summary: CT-based ORR assessed by IRC according to Lugano.

2.1.2 Secondary and Other Objectives, Endpoints

Secondary and other Objectives	Endpoints/Variables

 To assess the anti-tumor efficacy of AZD4205 using other CT-based efficacy endpoints in patients with r/r PTCL 	
 Duration of response (DoR), complete response rate (CRR), progression free survival (PFS), and time to response (TTR) assessed by IRC based on CT imaging, according to 2014 Lugano classification Investigators-assessed efficacy endpoints based on CT imaging per Lugano criteria, such as ORR, DoR, CRR, PFS, TTR

 To assess the safety and tolerability of AZD4205 in patients with r/r PTCL 	
 Adverse events (graded by CTCAE version 5.0)

 To characterize the PK of AZD4205 in plasma 	
 PK parameters derived from plasma concentrations of AZD4205
[REDACTED]	[REDACTED]

Statistical Analysis Plan of PTCL (Version 3.0)

[figure not shown]
Protocol Code: DZ2019J0005 (Part B)

Date: Mar 25, 2023

2.2 Overall Study Design

This is a phase I/II, open-label, multicenter study of AZD4205 administered orally in patients with r/r PTCL to determine its safety, tolerability, PK, and anti-tumor activity. The study design allows an escalation of dose with intensive safety monitoring to ensure the safety of the participants. The overall study includes Part A and Part B, and this SAP focuses on Part B only.

Figure 1 Study Flow Chart

Footnote: Eligible patients must have pathologically diagnosed PTCL, and have relapsed from or been refractory/intolerant to SoC
QD: once daily (dose frequency)

Part B of the study is designed as an open-label single arm cohort, which is planned to enroll around 100 participants with PTCL who have relapsed after or been refractory/intolerant to ≥ 1 (but not > 3) prior treatment regimen(s). The primary objective of this part is to evaluate anti-tumor efficacy of AZD4205 at recommended phase II dose (CT-based ORR assessed by IRC per Lugano criteria as primary endpoint) in patients with r/r PTCL. This part will also assess the safety, tolerability, PK, and anti-tumor efficacy (other endpoints) of AZD4205 at recommended phase II dose. Results of this part are planned to be used for marketing application of AZD4205 in patients with r/r PTCL.

This part of the study is composed of an initial screening phase, a single-arm treatment phase, a follow-up phase and a survival phase:

- Screening phase: Screening evaluations will be performed within 28 days prior to the first dose of study drug. Participants will sign the informed consent form prior to any screening evaluations. Please refer to Appendix A for details on screening procedures.
- Treatment phase: All participants will be treated with AZD4205 at 150 mg once daily, administered orally and will continue to be treated until disease progression, unacceptable toxicity, death, withdrawal of consent, or the study is terminated by the sponsor. A treatment cycle consists of 21 days. During treatment, CT scans of the same sites as screening will be done for tumor response assessment within 7 days of Day 1 of Cycle 3, 6, 9 and then every 3 cycles until PD or withdrawal from the study.
- Follow-up phase: A follow-up should be made after 28 days (± 7 days) following the last dose of the study treatment for safety follow-up.
- Survival phase: Participants will be followed up for survival via phone contact (with participant's guardian, if applicable) every 3 months after the participant's last visit until

Statistical Analysis Plan of PTCL (Version 3.0)

Protocol Code: DZ2019J0005 (Part B)

Date: Mar 25, 2023

withdrawal of consent, lost to follow-up, death, or the date of data cut-off for the final analysis.

2.3 Randomization

Not applicable.

2.4 Determination of Sample Size

For Part B dose expansion cohort, the assumption of IRC based ORR is 27%. With a sample size of 100 participants will have 84.5% power to reject the null hypothesis of ORR = 15% at 2-sided 5% significant level with binomial exact test. We referred to the null hypothesis in the pivotal study design of pralatrexate (O'Connor OA et al. 2011) and chidamide (Shi Y et al. 2015). With an observed ORR of 27% (27/100), the 95% exact CI is (18.6%, 36.8%).

3. ANALYSIS SET

3.1 All Participants

All participants screened (who signed informed consent form) will be included in this analysis set. It's mainly used for the individual data listing, and the overall summary of screen failures.

3.2 Safety Analysis Set

All participants treated with at least one dose of AZD4205 (all treated participants) will be included in the safety analysis set.

Safety analysis set is the primary analysis set for safety data, demographic data, exposure data.

3.3 Evaluable for CT-based Response Set

All dosed and central pathology confirmed PTCL participants with baseline measurable disease using CT imaging will be included in the evaluable for CT-based response set.

[REDACTED]

[REDACTED]

[REDACTED]

[REDACTED]

[REDACTED]

[REDACTED]

[REDACTED]

3.6 Evaluable for Survival Set

The evaluable for survival set will include all dosed and central pathology confirmed PTCL participants. This analysis set is mainly used for PFS [REDACTED] analysis.

3.7 Pharmacokinetics Set (PKS)

The pharmacokinetics set will include all dosed participants with at least one reportable AZD4205 plasma concentrations and no important adverse events or protocol deviations that may impact PK. The statistical analysis of PK data will be performed based on the PKS.

4. ENDPOINTS DEFINITION AND DERIVATION

4.1 Efficacy Endpoints

The efficacy endpoints based on the tumor assessments will be assessed according to the Lugano Classification for non-Hodgkin lymphoma (see Session 6.9 and Appendix VI of the CSP for details). The overall response for each participant may be provided from sources as illustrated below:

- For IRC-assessed efficacy endpoints: Final IRC-reported participant level overall response including Best Response, Date of Progression (if applicable), and Date of First Response (if applicable)
- For investigators-assessed efficacy endpoints: Investigator (local radiology) overall responses at each assessment/time point. Participant overall response date will be derived by program (see details in Section 4.1.2.5).

4.1.1 Primary Efficacy Endpoint

The primary efficacy endpoint is ORR, defined as the proportion of achieving either a PR or CR, which is assessed by IRC based on CT imaging, according to the Lugano Classification for non-Hodgkin lymphoma. Best overall response (BOR) (which contributes to the ORR) is defined as the best response recorded from date of first dosing until disease progression/recurrence or taking new anticancer therapy. Participants without post-baseline assessments to determine disease status will be classified as non-responders.

During treatment, CT scans of the same sites as screening will be done for tumor response assessment within 7 days of Day 1 of Cycle 3, 6, 9 and then every 3 cycles until PD or withdrawal from the study. Any other sites at which new disease is suspected should also be appropriately imaged. Any participant who discontinues study treatment for reasons other than disease progression should have response assessment performed as scheduled in the CSP until disease progression, or death occurs, unless consent is withdrawn.

Statistical Analysis Plan of PTCL (Version 3.0)

Protocol Code: DZ2019J0005 (Part B)

Date: Mar 25, 2023

4.1.2 Secondary Efficacy Endpoints

4.1.2.1 DoR assessed by IRC based on CT

DoR will be derived from those participants who had a CR or PR only.

DoR assessed by IRC based on CT is defined as the time from the date of first documented response until the date of documented progression or death due to any cause. Documented response and progression are both identified based on CT imaging evaluated by IRC. The end of response should coincide with the date of progression or death from any cause used for the PFS endpoint. The time of the initial response will be defined as the first visit response of PR or CR. If a participant does not progress following a response, then his/her duration of response will use the PFS censoring time.

The algorithm for DoR is provided below:

$$\text{DoR (months)} = (\text{date of event/censoring} - \text{date of first response} + 1) / 30.4375.$$

4.1.2.2 CRR assessed by IRC based on CT

CRR assessed by IRC based on CT is defined as the proportion of achieving CR, which is assessed by IRC based on CT imaging, according to the Lugano Classification for non-Hodgkin lymphoma.

4.1.2.3 PFS assessed by IRC based on CT

PFS is defined as the time from the date of first dosing until the date of objective disease progression as defined by Lugano classification or death (by any cause) regardless of whether the participant discontinues the study treatments. Progression is identified based on CT imaging evaluated by IRC. Participants who have not progressed or died at the time of analysis will be censored at the time of the latest date of assessment from their last evaluable tumor response assessment. More censoring rules for PFS are presented in Table 1. Symptomatic deterioration will not be regarded as a progression event.

The PFS will be calculated as:

$$\text{PFS (months)} = (\text{date of event/censoring} - \text{first dose date of AZD4205} + 1) / 30.4375.$$

Table 1 Censoring Scheme for PFS

No.	Situation	Date of Progression or Censoring	Outcome
1	No baseline or any post-baseline tumor assessments and without death within two visits (112 days from date of first dose)	Date of first dose	Censored

Statistical Analysis Plan of PTCL (Version 3.0)

Protocol Code: DZ2019J0005 (Part B)

Date: Mar 25, 2023

No.	Situation	Date of Progression or Censoring	Outcome
2	No baseline or any post-baseline tumor assessments and died within two visits (112 days from date of first dose)	Date of death	Event
3	Progression documented between scheduled visits	Date of first radiological PD	Event
4	No progression at the time of data cut-off/discontinuation from the study	Date of last visit with *adequate radiological tumor assessment prior to data cut-off or discontinuation from the study.	Censored
5	Treatment discontinuation for reason other than radiological PD	Data after discontinuation of treatment will be included when determining the time to progression	Event / Censored
6	New anticancer treatment started	Date of last adequate radiological tumor assessment with documented non-progression before start of new treatment	Censored
7	Death before first PD assessment	Date of death	Event
8	Death between scheduled tumor assessment visits	Date of death	Event
9	Death or progression after more than one missed visit (CT scans will be done for tumor assessments within 7 days of Day 1 of Cycle 3, 6, 9 and then every 3 cycles thereafter until PD)	Date of last adequate radiological tumor assessment with documented non-progression	Censored

* Adequate tumor assessment is a radiologic assessment of CR, PR, SD, non-CR/non-PD or PD as determined by investigators.

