- Survival phase: Patients will be followed up for survival via phone contact (with patient's guardian, if applicable) every 3 months after the patient's last visit until withdrawal of consent, lost to follow-up, death, or the date of data cutoff for the final analysis. The investigator or his/her designee will also continue to collect information on new anticancer therapy given after the last dose of study drug. Subjects lost to follow up should also be recorded on the CRF. The status of ongoing, withdrawn (from the study) and "lost to follow-up" subjects at the time of an OS analysis should be obtained by the site personnel by checking the subjects notes, hospital records, contacting the subjects general practitioner and checking publicly available death registries. In the event that the subject has actively withdrawn consent to the processing of their personal data, the vital status of the subject can be obtained by site personnel from publicly available resources where it is possible to do so under applicable local laws.

[figure not shown]
For the primary efficacy analysis, tumor response will be evaluated by an IRC based on central imaging assessment according to Lugano criteria (Cheson BD et al. 2014).

All patients should undergo contrast CT scan and bone marrow aspiration/biopsy at screening. During treatment, CT scans of the same sites as screening will be done for tumor response assessment within 7 days of Day 1 of Cycle 3, 6, 9 and then every 3 cycles until PD or withdrawal from the study. Bone marrow aspiration or biopsy is required to confirm a complete response for patients with bone marrow disease involvement at baseline (screening).

PET scan, where available, needs to be performed at screening for baseline tumor metabolism assessment. For patients with FDG-avid disease at baseline, PET should be reexamined for metabolic response assessment on Day 1 of Cycle 3, and when clinically need to confirm a complete metabolic response (CMR). Patients with confirmed CMR are not required to undergo further PET scans on study unless there is suspicion of progressive disease. If disease is not FDG-avid at baseline, PET scan is not required for efficacy assessment after study treatment initiates.

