Subjects who are discontinued from study drug for any reason (i.e., AE or administrative reasons etc.) other than disease progression should not be considered withdrawn from the study. They will continue to be followed for efficacy evaluations per schedule outlined in Table 3 until subject exhibits first progression, withdrawal of consent, death, lost to follow-up, or study termination from sponsor, whichever occurs first. If subjects refuse to return for these visits or are unable to do so, every effort should be made to contact them or obtain information by telephone to determine the subject's disease status and survival.

Figure 2 Schema for dose expansion study (Part B)

Abbreviations: PTCL, peripheral T cell lymphoma; PO orally taken; EOT, end of treatment; PD, progressive disease

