6.9.3 Disease assessment

If an unscheduled assessment is performed and the patient has not progressed, every attempt should be made to perform the subsequent assessments at their scheduled visits.

In the event disease progression is suspected due to physical examination or laboratory test, a CT and/or PET scan must be performed to confirm disease progression. If medically appropriate, it is recommended that uncertain disease progression should be confirmed by an alternative diagnostic imaging modality or biopsy, e.g. diagnostic quality CT/biopsy to confirm metabolic disease progression, or cytologic test to confirm malignant effusion. If the investigator is in doubt as to whether progression has occurred, it is advisable to continue treatment until the next scheduled assessment or sooner if clinically indicated and reassess the patient's status. If repeated scans confirm progression, then the date of the initial scan should be declared as the date of progression.

It is important to follow the assessment schedule as closely as possible. Please refer to the study plan (Table 2 and Table 3).

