6.9.5.1 Progression free survival follow-up

Patients' tumor response should be followed according to the study plan (Table 2 and Table 3) till confirmed disease progression per Lugano criteria, death or withdrawal of consent. Under circumstances of dose discontinuation for reasons other than progression, response assessments should be continued per study plan until confirmed disease progression.

Beyond the 28-day follow up visit only subsequent cancer therapy and response assessment (if applicable) should be collected.

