7.5.1 Objective response rate

The ORR is defined as the proportion of achieving either a PR or CR, according to the Lugano Classification for NHL (Cheson BD et al. 2014). In Part A, the ORR is assessed by investigators.

In Part B, the ORR will be assessed by both an IRC and investigators, while the results by IRC will be used as primary assessment for analysis of primary endpoint, and a concordance analysis will be performed to compare the results by IRC and investigators.

The response of the PTCL to treatment must be consistent with clinical guidelines (Cheson BD et al. 2014) as listed in Table 9.

Overall response assessments will include evaluation of physical exams, bone marrow assessments, and radiographic evaluations per the Schedule of Assessments (see Table 2 and Table 3). Patients who have signs and symptoms of progression outside of the scheduled assessment should be evaluated by the investigator with a physical exam and laboratory assessments to determine if disease progression is present. In the event disease progression is suspected due to physical examination or laboratory test, a CT and/or PET scan must be performed to confirm disease progression. If medically appropriate, it is recommended that uncertain disease progression should be confirmed by an alternative diagnostic imaging modality or biopsy, e.g. diagnostic quality CT/biopsy to confirm metabolic disease progression, or cytologic test to confirm malignant effusion.

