5.5.3 Sensitivity Analysis

No sensitivity analysis will be conducted.

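### Part B does not say whose progression ends imaging, while IRC PFS and DoR count only IRC CT progression, so site-called progressions that the IRC does not call may be censored informatively, with no sensitivity analysis planned.

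*SAP*

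**What the plan says.** **When imaging ends.** Protocol 3.1.3 schedules Part B CT at "Cycle 3, 6, 9 and then every 3 cycles until PD or withdrawal from the study". Patients who stop drug for another reason are followed for efficacy "until subject exhibits first progression, withdrawal of consent, death, lost to follow-up, or study termination from sponsor". Protocol 6.9.5.1 follows tumor response "till confirmed disease progression per Lugano criteria, death or withdrawal of consent", and Appendix VI also speaks of confirmed progression. None of these places names the assessor or the confirmer.

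**How a site establishes progression.** Outside scheduled visits, patients with signs of progression "should be evaluated by the investigator with a physical exam and laboratory assessments to determine if disease progression is present" (Protocol 7.5.1). Where progression is suspected, "a CT and/or PET scan must be performed to confirm disease progression" (Protocol 6.9.3). Checking a metabolic progression by CT or biopsy is recommended, not required.

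**What counts as an event.** SAP 4.1.2.3 says of PFS: "Progression is identified based on CT imaging evaluated by IRC". Death is the only other event. DoR takes its end date and its censoring from PFS (SAP 4.1.2.1).

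**How others are censored (SAP Table 1).**
- Row 4, no progression: the last adequate radiological assessment.
- Row 6, new anticancer treatment: the last adequate assessment with documented non-progression before it. Protocol 6.9.1 says images after new therapy are not collected.
- Rows 7 and 8: deaths are events. Row 9 censors a death or progression that follows more than one missed visit.
- The footnote leaves adequacy to the investigator and lists PD among adequate readings, although the table serves an IRC endpoint.

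**Sensitivity.** SAP 5.5.3: "No sensitivity analysis will be conducted".

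**The concern.** The progression that can end imaging and the progression that counts as an event need not be the same. If the site calls progression and the IRC does not call it on that CT, nothing in the protocol or SAP keeps scans going until the IRC does. With no later scan, row 4 censors the patient. With new therapy, row 6 does, and later images do not exist.

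Kaplan-Meier assumes that a censored patient has the same future risk as those still followed. A patient whom a site has just judged to be progressing may well have a higher one, and the estimate would then be too high. Part B is a single-arm cohort planned to support a marketing application (Protocol 3.1.3), so no control arm would share the bias. Protocol 2.1 puts PFS on existing treatment at 3 to 4 months.

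The footnote adds a contradiction: a scan that the investigator read as PD can supply the censoring date for an IRC endpoint.

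**Working it through.** **1. The plan's own figures.** The documents give no sample size or power for PFS or DoR. The ORR figure reproduces: with n = 100 and a null of 15%, the smallest count with an upper tail of at most 0.025 is 23 (tail 0.0221), and the power at 27% is 0.8448, the stated 84.5%. Table 1's 112 days is (6 − 1) × 21 + 7 = 112.

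**2. Scan grid.** Cycle 3 Day 1 falls (3 − 1) × 21 = 42 days after first dose and Cycle 6 Day 1 at 105 days. Scans then follow every 63 days: 168, 231, 294, 357. The last scan before 12 months is at day 357.

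**3. Hand calculation.** Assumptions, none from the documents: exponential time to site-called progression with median m months; a share q of those progressions not called by the IRC; unconfirmed cases become IRC progressions at the next scan; no deaths; scans on schedule. Let S(t) = 0.5^(t/m), h1 = 1 − S(42 days) and h = 1 − S(63 days), with 30.4375 days per month.

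- Imaging continued to IRC progression: PFS at 12 months = S(357) + q[S(294) − S(357)].
- Censored at the site's scan: [1 − (1 − q)h1] × [1 − (1 − q)h]^5.

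For m = 6: h1 = 0.147, h = 0.213, S(294) = 0.328, S(357) = 0.258. At q = 20%, continued = 0.258 + 0.2 × 0.070 = 0.272; censored = (1 − 0.8 × 0.147)(1 − 0.8 × 0.213)^5 = 0.347.

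For m = 3.5: h1 = 0.239, h = 0.336, S(294) = 0.148, S(357) = 0.098.

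| q | m = 3.5, continued vs censored | m = 6, continued vs censored |
|---|---|---|
| 10% | 10.3% vs 12.9% | 26.5% vs 30.0% |
| 20% | 10.8% vs 16.9% | 27.2% vs 34.7% |
| 30% | 11.3% vs 21.8% | 27.9% vs 40.1% |

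**4. With deaths and the visit window.** The hand calculation omits deaths, which remain events. Simulation with 15% of events as deaths and scans spread over ±7 days gives smaller gaps:

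| q | m = 3.5, continued vs censored | m = 6, continued vs censored |
|---|---|---|
| 10% | 10% vs 12% | 26% vs 29% |
| 20% | 11% vs 15% | 27% vs 33% |
| 30% | 11% vs 18% | 28% vs 37% |

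The overstatement is about 2 to 9 points. For m = 3.5 the Kaplan-Meier median is 5.3 to 5.4 months continued and 5.3 to 5.6 censored, so censoring adds about 0.1 month. Both exceed 3.5 because progression is dated to scans. For m = 6 with fixed scan dates, the median can jump one scan interval, from 7.6 to 9.7 months, at 20 to 30%.

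**5. If many unconfirmed cases die first.** If 30% of unconfirmed cases die before the next visit without new therapy (fixed dates, m = 6), the contrast is 27% vs 32% at q = 20% and 28% vs 36% at q = 30%.

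**6. If unconfirmed cases carry average risk.** With fixed dates and no deaths, m = 6 gives 34% vs 35% at q = 20% and 38% vs 40% at q = 30%. For m = 3.5 it gives 16% vs 17% and 18% vs 22%. With deaths and the visit window, the gap is about 1 point or less.

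**7. DoR.** Take an assumed 12-month median, response at the first scan and scans every 63 days afterwards, under the assumptions of step 3. Then h = 0.113, and the 12-month rate is S(315) + q[S(252) − S(315)] if continued and [1 − (1 − q)h]^5 if censored. This gives 55.7% vs 58.6%, 56.4% vs 62.4% and 57.1% vs 66.3% at q = 10, 20 and 30%. Under average risk the gap is at most 1 point.

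**The case against.** Several stronger readings are tempting, and the documents do not support them.

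- **Imaging stops at the investigator's progression.** This is a reasonable inference, not text. The Independent Review Charter, which the SAP cites, is not available here and might require IRC confirmation.
- **Every such patient is censored at that scan.** Deaths remain events under rows 7 and 8 unless row 9 applies. With new therapy, row 6 read with the investigator-based footnote points to the scan before the site's progression; read on IRC results it points to that scan. After a PET-only call the last CT may be earlier.
- **Both endpoints are inflated.** This is not shown. No discordance rate is given, and step 6 shows that the direction and size depend on the risk of the unconfirmed cases.
- **The median grows in proportion to the discordance.** Scaling the hazard by (1 − q) compares an investigator median with an IRC estimate, which mixes reader disagreement with censoring bias. The proper comparator is IRC PFS with imaging continued, and there a short median hardly moves.
- **The nine-week scan spacing is a further defect.** Dating progression to scans is standard practice, and DoR onset is scan-dated too, so delays largely offset.

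The protocol also has safeguards. Section 6.9.3 advises continuing and reassessing when the investigator is in doubt, and recommends a second modality or biopsy for uncertain progression. Section 5.3.1 allows treatment past progression where there is benefit. On-treatment PET is limited, so PET-only calls should be few. Investigator CT-based PFS and DoR are planned secondary endpoints (SAP 4.1.2.5), and an IRC-investigator comparison is planned (Protocol 6.9.4.2).

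These points narrow the concern but do not close it. The safeguards are advisory. The investigator endpoints omit PET-only progressions and change responders and dates together. The concordance analysis is described for ORR (Protocol 3.2.2, 7.5.1), and nothing re-examines the censored IRC times.

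**Conclusion.** The point holds as a gap in the plan, not as a demonstrated bias. Imaging may end on a progression that the IRC endpoints do not recognise, the censoring that follows may be informative, and no analysis tests it.

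The effect falls mainly on later landmark rates. The 2 to 9 point figure for 12-month PFS assumes 10 to 30% discordance, exponential times, 15% of events as deaths, and unconfirmed cases progressing at the next scan. It shrinks almost to nothing if those cases carry average risk. The primary ORR endpoint and its 84.5% power are not affected. The footnote mismatch needs correction whatever the discordance turns out to be.

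**What to change.** 1. Replace SAP 5.5.3 with a pre-specified sensitivity analysis of IRC PFS and DoR. Count a site-called progression (CT or PET) without IRC progression as an event on the site's date. New anticancer therapy started after that call should not turn it back into a censored observation.
2. In the SAP Table 1 footnote, tie adequacy to the IRC read for IRC endpoints and to the investigator read for investigator endpoints. This also settles which scan row 6 means.
3. Reconcile Protocol 3.1.3, 6.9.1, 6.9.3, 6.9.5.1 and Appendix VI on whose progression, and on which modality, ends Part B imaging. If the charter already settles this, refer to it.

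The cost is one extra set of tables from data already collected, some wording changes, and possibly a less favourable supportive estimate to report beside the main one.
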